### 10.1.1 Potential harm monitoring

[Heyse et al. \(2008\)](#) and the HVTN 505 Phase 2b HIV-1 vaccine efficacy trial ([Hammer et al., 2013](#)) are examples of randomized, placebo-controlled efficacy trials that used continuous monitoring for an elevation in the endpoint rate in the active versus control treatment arm. Continuous monitoring means that an unblinded statistician has visibility to the treatment assignment of each diagnosed MITT HIV-1 infection as they are determined in real-time, and, after each confirmed HIV-1 infection diagnosis, this statistician notes whether a stopping boundary is reached that indicates that the relative cumulative rate of HIV-1 infection (RR, vaccine/placebo) exceeds one. If the stopping boundary is met, then the unblinded statistician immediately informs the Chair of the DSMB and the Executive Secretary of the DSMB through secure communication procedures. As such, the potential harm monitoring is in real-time, with a result possible at any time, whereas in contrast the non-efficacy and high efficacy monitoring is conducted only at the 6-monthly scheduled DSMB meetings

Table 5: Summary of interim monitoring of VE

Monitoring Outcome	Hypotheses	Testing Approach	Size	Monitoring Plan	Timing of Interim Analyses
Potential Harm	$H_0 : VE(0-24) \geq 0\%$ vs. $H_1 : VE(0-24) < 0\%$	Exact 1-sided binomial test of the proportion of infections assigned to vaccine group	1-sided $\alpha = 0.05$	Near-constant* 1-sided p-value cut-off controlling the FWER at $\alpha = 0.05$	After every MITT infection from 10 th total until first non-efficacy analysis
Non-Efficacy	$H_0 : VE(0-24) \geq 40\%$ vs. $H_1 : VE(0-24) < 40\%$ and $H_0 : VE(7-24) \geq 40\%$ vs. $H_1 : VE(7-24) < 40\%$	Wald test	1-sided $\alpha = 0.025$	Unadjusted 95% CIs for VE(0-24) and VE(7-24): lower bounds $< 0\%$ and upper bounds $< 40\%$	6-monthly starting once all participants reach 13 months, and 60 MITT infections are observed, then through the end of Stage 1
High Efficacy	$H_0 : VE(0-36) \leq 70\%$ vs. $H_1 : VE(0-36) > 70\%$	Wald test	1-sided $\alpha = 0.025$	Unadjusted 95% CI for VE(0-36): lower bound $> 70\%$	Harmonized with non-efficacy monitoring, starting when 150 MITT participants reach 36 months of follow-up; if Stage 2 occurs, 1 additional analysis halfway through Stage 2

\*An increasing per-test alpha until a constant level is reached that, if applied to all subsequent tests, maintains the specified FWER (see Table 6)

through the end of Stage 1 or at any extra DSMB meetings requested by the DSMB (with the exception that the first non-efficacy analysis would be done and reported to the DSMB by secure means at the time when all participants in follow-up reach 13 months of follow-up, and 60 total MITT primary endpoint events are observed).

The potential harm monitoring is done using an exact one-sided binomial test of the null hypothesis  $H_0 : p \leq 1/2$  versus the alternative hypothesis  $H_1 : p > 1/2$ , where  $p$  is the probability that an HIV-1-infected participant was assigned to the vaccine group (as compared to being assigned to the placebo group). The tests start at the 10th total infection and are performed continuously until the non-efficacy monitoring commences. Each test is performed at a prespecified nominal/unadjusted alpha-level, which may vary over the multiple tests. The alpha-level used for each test is determined indirectly as follows: first, we choose the overall type I error rate we are willing to accept over the course of the monitoring (the overall probability that we reach a stopping boundary during the trial when the vaccine regimen is actually safe, i.e., true  $RR = 1$ , equivalently  $p = 1/2$ ); and second, we choose whether/how to vary the alpha-level from test-to-test. Using these pieces of information we determine the exact alpha-levels to be used for each test.

Table 6: Potential harm monitoring stopping boundaries: One-sided p-value cut-offs for rejecting  $H_0 : p \leq 1/2$  in favor of  $H_1 : p > 1/2$  with an exact 1-sided binomial test where  $p$  is the probability that an HIV-1-infected participant was assigned to the vaccine group

No. of Infections in Vaccine Group	No. of Infections in Placebo Group	Per-Test Type I Error Rate (1-Sided P-value Cut-off)
10	0	0.011
10	1	0.014
11	2	0.014
13	3	0.014
15	4	0.014
16	5	0.014
18	6	0.014
20	7	0.014
21	8	0.014
23	9	0.014
24	10	0.014
26	11	0.014
27	12	0.014
28	13	0.014
30	14	0.014
31	15	0.014
33	16	0.014
34	17	0.014
35	18	0.014
37	19	0.014
38	20	0.014
39	21	0.014

An overall 1-sided type I error rate of 0.05 is chosen for the family-wise error rate of the multiple hypothesis tests starting at the 10th HIV-1 infection endpoint through to the 60th. This type I error rate is chosen to balance the competing goals of participant safety and preventing false positive results. To prevent stopping too early, perhaps due to spurious results caused by wide sampling variability, stopping prior to the accumulation of 10 total infections was ruled out. Table 6 shows the potential harm stopping boundaries in terms of the one-sided p-value cut-offs for a selected set of potential harm interim analyses starting at the 10th HIV-1 infection event.

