6.5 Trial monitoring

The trial will be formally monitored. This may lead to a modification or termination of the trial.

Table 6-3 lists the specification of parameters under which the power calculations were done. The details of the actual monitoring plan will be discussed in the Statistical Analysis Plan (SAP). Table 6-4 provides the different outcome probabilities when applying these sequential monitoring rules to the study, assuming an incidence of 4.2%. More details on the individual monitoring rules follow in the subsequent sections.

Table 6-3 Sequential monitoring specifications used for power calculations

Monitoring Type	Hypotheses	Statistical Method	Monitoring Plan	Timing of Analyses
Potential Harm	H0: VE(0-24) ≥ 0% vs. H1: VE(0-24) < 0%	Exact 1-sided binomial test of the fraction of infections assigned to receive the vaccine.	Constant p-value cut- off controlling the FWER at α=5%	After every MITT infection starting by the 10 th infection until the first non-efficacy analysis
Non- Efficacy	H0: $VE(0-24) \ge 40\%$ H0: $VE(7-24) \ge 40\%$ vs. H1: $VE(0-24) < 40\%$ H1: $VE(7-24) < 40\%$	For both VE(0-24) and VE(7-24): LCLs of 95% CI<0% and	Unadjusted 95% confidence intervals around VE(0-24) and VE(7-24)	6-monthly starting once all participants reach Month 13, and 60 MITT infections are observed, then through the end of Stage 1
High Efficacy	H0: VE(0-36) ≤ 70% vs. H1: VE(0-36) > 70%	completely above 70%	Unadjusted 95% confidence interval around VE(0-36)	Harmonized with non-efficacy monitoring starting when 150 participants reach 36 months of follow-up. If Stage 2 occurs, one additional analysis half- way through Stage 2

Table 6-4 Outcome probabilities under sequential monitoring of vaccine efficacy

True VE(7-24)	Potential Harm	Non-efficacy (interim)	High Efficacy	UC Power (PP) (end	UC Power (MITT) (end
	4.57.0/	01.10.0/	0.00/	Stage 1)	Stage 1)
0	4.57 %	81.18 %	0.0%	2.18 %	2.18 %
10	2.88 %	65.97 %	0.0%	7.19 %	7.41 %
20	1.70 %	41.08 %	0.0%	20.17 %	21.79 %
30	0.90 %	19.32 %	0.0%	43.33 %	45.80 %
40	0.64 %	5.55 %	0.0%	69.90 %	73.10 %
50	0.31 %	1.26 %	0.0%	90.86 %	91.58 %
60	0.21 %	0.14 %	0.02 %	98.58 %	98.70 %
70	0.14 %	0.00 %	0.13 %	99.92 %	99.83 %
80	0.04 %	0.00 %	1.20 %	99.99 %	99.95 %
90	0.03 %	0.00 %	8.26 %	100.0%	99.97 %

In the simulations, the start of the non-efficacy and high-efficacy monitoring was set to assure that the trial was continued to be monitored for harm until the M13 time point under the trial pre-trial assumptions:

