6.5.1 Monitoring for potential harm

The unblinded statistician will continuously monitor the trial for early evidence of a higher infection rate of MITT HIV-1 infection in the vaccine group compared to the placebo group to ensure participant safety. The monitoring will start from the 10th infection onward

VE halved in first 7 months

N=1300:1300 placebo:vaccine group

^{4.2%} annual incidence in placebo group 10% annual dropout 5% missed vaccinations

(pooled over vaccine and placebo) and after each additional infection it is decided whether the stopping boundary has been reached [VE(0-24)<0%]. It will continue until the first analysis for non-efficacy is performed. The potential harm monitoring uses the one-sided exact binomial test resulting in a boundary that is determined via controlling the overall type I error rate across tests at 5%. Figure 6-3 shows for example that when 60 infections are counted, with 40 infections in the active vaccine arm, the boundary has been reached. In general, the null hypothesis will be rejected when the probability that the observed infections are from the vaccine arm is significantly larger than 50% (blue line in Figure 6-3). If the prespecified stopping boundary is reached, then the unblinded statisticians will immediately inform the DSMB. In addition, the DSMB chair will be updated on the accruing unblinded HIV-1 infection data after each confirmed MITT infection. This monitoring guideline is chosen to allow stopping for prudence as early as possible, maximizing participant safety.

[figure not shown]

Figure 6-3 Potential harm stopping boundary for the total number of HIV-1 infections in the active vaccine regimen versus placebo. Blue line is the potential harm stopping boundary, red line displays the case that all of the infections are in the vaccine arm.

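### SAP Table 6 is inconsistent as printed at the 10th infection (9:1 meets the 0.011 cut-off but not the 10:0 count), and the protocol's description and example of the harm boundary do not quite match the SAP's

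*SAP*

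**What the plan says.** SAP 10.1.1 sets out the harm rule. "The potential harm monitoring is done using an exact one-sided binomial test of the null hypothesis" that an infection is no more likely to fall in the vaccine arm than in the placebo arm. On error control, the section states: "An overall 1-sided type I error rate of 0.05 is chosen for the family-wise error rate". It describes the looks that this covers as "multiple hypothesis tests starting at the 10 th HIV-1 infection endpoint through to the 60 th". Each test has its own nominal level.

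Table 6 is headed "Potential harm monitoring stopping boundaries: One-sided p-value cut-offs for rejecting", and the section presents it as the boundary expressed through one-sided cut-offs at selected analyses. Each row gives a vaccine count, a placebo count and a cut-off. The first row is 10:0 at 0.011, the second is 10:1 at 0.014, and the last is 39:21 at 0.014.

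SAP Table 5 calls the cut-off near-constant, with this footnote: "An increasing per-test alpha until a constant level is reached that, if applied to all subsequent tests, maintains the specified FWER".

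Protocol Table 6-3 describes the same rule as "Constant p-value cut- off controlling the FWER at α=5" per cent. Protocol 6.5.1 adds a worked example from its Figure 6-3: "when 60 infections are counted, with 40 infections in the active vaccine arm, the boundary has been reached". Protocol 6.5 introduces Table 6-3 as the specification behind the power calculations and leaves the actual monitoring plan to the SAP.

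**The concern.** This is the trial's one real-time stopping rule. When the boundary is met, the unblinded statistician must tell the DSMB at once. A prespecified trigger of this kind should give one answer for any observed split.

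As printed, Table 6 does not do so at the first look. By the count columns, 9:1 does not stop. By the cut-off column, 9:1 does. The text of SAP 10.1.1 defines each test by its nominal level, so a careful reader could reasonably take the cut-off column as the rule.

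The protocol also describes a differently shaped cut-off (constant rather than near-constant) and illustrates the boundary at 60 infections with a count one higher than the SAP's. A reader with both documents cannot tell whether they are meant to describe the same boundary.

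**Working it through.** **Inputs.** The boundary counts and cut-offs come from SAP Table 6. The looks are after each infection from the 10th to the 60th (SAP 10.1.1), which makes 51 looks. The overall one-sided error is 0.05 (SAP 10.1.1). Under the null, p = 1/2. The constant cut-off comes from Protocol Table 6-3 and the 40-of-60 example from Protocol 6.5.1.

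**Formulas.** The per-test p-value for v vaccine infections among n is P(X ≥ v) with X ~ Binomial(n, 1/2).

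For the family-wise error, let q_n(k) be the probability of k vaccine infections among n with no earlier crossing. Then q_{n+1}(k) = ½·q_n(k) + ½·q_n(k−1). From n = 10 on, the mass at or above the boundary count is removed and added to the error.

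**1. Reproduce the SAP's figure.** With the Table 6 counts as the rule, the family-wise error over looks 10 to 60 is 0.0499. This agrees with the stated 0.05.

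**2. Check the rows.**
- n = 10, 10:0: p = 1/1024 = 0.00098.
- n = 10, 9:1: p = (10 + 1)/1024 = 0.01074, which is below the printed 0.011. The printed cut-off therefore admits 9:1.
- n = 60, 39:21: p = 0.01367, below 0.014. At 38 of 60, p = 0.02595, above 0.014. The count and cut-off agree.
- The remaining rows also agree with 0.014.

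**3. Apply the printed cut-offs literally** (0.011 at n = 10, 0.014 afterwards). The boundary moves to 9:1 at n = 10 and is otherwise unchanged. The family-wise error becomes 0.0526, above 0.05. The chance of a false stop at the first look rises from 0.10% to 1.07%, but the overall error rises by only 5.26 − 4.99 = 0.27 percentage points. Most paths through 9:1 cross the boundary later in any case, for example at 10:1 on the next infection.

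**4. Rounding.** Any level from 0.0105 to just under 0.01074 prints as 0.011 at three decimals and still requires 10:0. With 0.0106 at n = 10 and 0.014 afterwards, the Table 6 boundary is reproduced at all 51 looks, with error 0.0499.

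**5. A constant cut-off.** The protocol prints no value, so one has to be solved for. Over looks 10 to 60, the largest constant cut-off with error at or below 0.05 lies between 0.01295 and just under 0.01330, with error 0.0492. It requires 40 of 60, because P(X ≥ 40) = 0.00674 passes and P(X ≥ 39) = 0.01367 does not. This matches the 6.5.1 example.

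On that assumed horizon, the constant rule and Table 6 differ by one infection at five of the 51 looks:

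| Total infections | Constant rule | SAP Table 6 |
|---|---|---|
| 10 | 9 | 10 |
| 21 | 17 | 16 |
| 41 | 29 | 28 |
| 53 | 36 | 35 |
| 60 | 40 | 39 |

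**6. Sensitivity to the horizon.** The 10-to-60 range is the SAP's. The protocol ends harm monitoring at the first non-efficacy analysis and states no cap at 60. With horizons of 70 and 80 infections the constant rule still starts at 9:1. At 100, 120 and 150 it starts at 10:0, as in the SAP. It requires 40 at n = 60 for every horizon tried from 60 to 150.

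**The case against.** The strongest reply is that nothing is wrong with the boundary itself. Table 6 is titled as stopping boundaries and prints 10:0, so it answers the 9:1 question directly. The cut-off column is a three-decimal display, and the Table 5 footnote explains why the first level is lower than the rest. The 5.26% arises only if a rounded number overrides the counts beside it. This largely stands: the counts are sound and rounding is the likely cause. It does not remove the defect, because the SAP text defines the tests by their levels and nowhere says that the counts take precedence.

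A reader might infer that the protocol sets a rival boundary that starts at 9:1 and conflicts with the SAP at five totals. The documents do not support that. The protocol gives no cut-off value and no count table, its Figure 6-3 is not shown in the text available, and it assigns the actual plan to the SAP. The 9:1 start and the list of five totals depend on lending the SAP's 10-to-60 horizon to the protocol's rule.

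A reader might also take 40 against 39 as a flat contradiction. It is not one: 40 of 60 crosses a boundary of 39 too, and the protocol offers it as an example without saying that 39 would fail. What stands is that a constant 5% cut-off yields exactly 40, so the example probably illustrates a boundary other than the one in Table 6.

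The practical effect is also small. The DSMB chair is updated on unblinded infections after each confirmed MITT infection (Protocol 6.5.1), so a 9:1 split would be seen in any event. At a true vaccine-to-placebo rate ratio of 2, the chance of crossing by 60 infections is 75.0% with Table 6 and 72.6% with the reconstructed constant rule.

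**Conclusion.** The point holds as a minor inconsistency. The first row of Table 6 gives two answers for 9:1: the counts hold the family-wise error at 4.99%, and the printed cut-offs give 5.26% against a stated 5%. This is exact arithmetic on printed figures and assumes only looks at infections 10 to 60, the range that the SAP states for its error control.

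The stronger inference, that the harm rule fails to control its error, is not supported, because the counts reproduce the stated level. The 11-fold contrast in false-stop probability (1.07% against 0.10%) describes one look only and overstates the overall effect, which is 0.27 percentage points.

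The protocol mismatch is real in description (constant against near-constant) and in the position of the illustrated boundary at 60 infections (40 against 39). It is minor because the SAP governs by the protocol's own terms. The count of five differing looks is conditional on an assumed horizon and should not be cited as a documented difference.

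**What to change.** 1. State in SAP 10.1.1 that the Table 6 counts are the operative stopping rule.
2. Print the cut-offs to at least four decimals so that they reproduce those counts. The first must lie below 0.01074. The value actually used should be taken from the boundary program; the 0.0106 used above is only illustrative.
3. Align Protocol Table 6-3 (constant or near-constant) and the 6.5.1 example with the SAP boundary, preferably by reference to Table 6.

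The cost is a table correction in the SAP and a protocol clarification memo. No design quantity changes.

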## 6 Interactions of Study Statisticians with the Data and Safety Monitoring Board

At each 6-monthly Data and Safety Monitoring Board (DSMB) meeting, the study statisticians will present Open, Chair/Medical Officer, and Closed Reports; all tables and figures included in the Closed Report are specified in Appendix A with statistical analyses of safety further described in Section 7. For a subset of tables and figures in the Closed report, the Open Report includes tables and figures with the same information except with trial information presented pooled across the two treatment groups to preserve blinding to treatment assignment. In addition, the following interim monitoring reports will be presented at each DSMB meeting:

- monitoring report of vaccine efficacy for potential harm, non-efficacy, and high efficacy per Section 10.1, where
  - potential harm monitoring starts at the 10th pooled MITT infection endpoint and is continually performed with each additional endpoint until the time non-efficacy/high efficacy monitoring is triggered,
  - non-efficacy monitoring starts at the 60th pooled MITT infection and proceeds at every scheduled DSMB meeting thereafter (anticipated every six months) until the end of Stage 1, and
  - high efficacy monitoring is harmonized with non-efficacy monitoring and starts when 150 MITT participants reach their Month 36 visit (end of Stage 2); if Stage 2 occurs, one additional high efficacy interim analysis will be performed at 6 months after the end of Stage 1;
- monitoring of the use of Truvada as pre-exposure prophylaxis (PrEP) first reported for the April 2019 DSMB meeting per Section 10.2;
- monitoring report for futility to assess vaccine efficacy per Section 10.3 starting at the latest 12 months after the first participant is enrolled and continuing every 6 months thereafter; and
- monitoring report for performance standards of quality of trial conduct per Section 10.4.

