### 10.1.2 Non-efficacy monitoring

The DSMB will monitor the vaccine for non-efficacy defined as evidence that it is highly unlikely that the vaccine has a beneficial effect on acquisition of VE(0–24) or of VE(7–24) of 40% or more. Such analyses will start when two conditions are met: (1) all participants in follow-up have reached 13 months of follow-up since enrollment, and (2) at least 60 MITT infections have been observed. Condition (2) is chosen as the minimum MITT infection total at which a point estimate of zero VE would just correspond to an unadjusted upper 95% confidence bound for VE(0–24) equal to 0.40 based on a Cox proportional hazards model; the approach, stated in condition (2), to starting non-efficacy monitoring was suggested by [Freidlin, Korn, and Gray \(2010\)](#). Thereafter, non-efficacy interim analyses will proceed at every scheduled DSMB meeting (anticipated every six months) until the end of Stage 1.

The criterion for non-efficacy is that, for both VE(0–24) and VE(7–24), the lower 95% confidence bound lies below 0% and the upper 95% confidence bound lies below 40%. By checking confidence intervals for both VE(0–24) and VE(7–24), and requiring completed 13 months of follow-up, the monitoring plan is designed to protect against stopping prematurely based on ramping vaccine efficacy over the intercurrent period of 0–13 months.

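### The harm boundary in SAP Table 6 holds the error at 5% only to infection 60, but harm testing now runs until all participants reach Month 13; carried forward, its cut-off gives about 7%

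*SAP*

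**What the plan says.** SAP 10.1.1 tests the vaccine share of infections with an exact one-sided binomial test after every MITT infection from the 10th. The error statement is explicit: an overall one-sided rate of 0.05 is set for "the family-wise error rate of the multiple hypothesis tests starting at the 10 th HIV-1 infection endpoint through to the 60 th". Table 6 lists the boundary from 10 vaccine / 0 placebo to 39 vaccine / 21 placebo, which is infection 60. The cut-off is 0.011 in the first row and 0.014 in all others.

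The footnote to Table 5 describes the 0.014 as a constant level that, "if applied to all subsequent tests, maintains the specified FWER", and refers the reader to Table 6.

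The horizon is given differently elsewhere:

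- SAP 10.1.1: the tests begin at the 10th "total infection and are performed continuously until the non-efficacy monitoring commences".
- SAP 10.1.2: "Such analyses will start when two conditions are met: (1) all participants in follow-up have reached 13 months of follow-up since enrollment", with at least 60 MITT infections as the second condition. SAP Table 5 and Protocol Table 6-3 agree.
- SAP section 6: non-efficacy monitoring starts at the 60th "pooled MITT infection and proceeds at every scheduled DSMB meeting thereafter (anticipated every six months) until the end of Stage 1", with no 13-month condition. The same list ends harm monitoring when non-efficacy or high-efficacy monitoring is triggered.
- Protocol 6.5: in the simulations behind Table 6-4, "the trial was continued to be monitored for harm until the M13 time point". That table gives a 4.57% probability of a harm stop at VE = 0.
- Protocol 6.5.1: the test results in "a boundary that is determined via controlling the overall type I error rate across tests at 5" percent.

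**The concern.** The 5% is calibrated over one range of infections and the tests are run over a longer one. Repeated testing at a fixed per-test level keeps adding error, so a boundary that uses its full 5% by infection 60 must exceed 5% if testing continues at the same level.

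SAP 10.1.1 defines the overall error as the chance of reaching a boundary at any point in the monitoring of a safe vaccine, so an error fixed at infection 60 does not meet the SAP's own definition. It also says that 5% was picked to balance participant safety against false positives.

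Crossing the boundary sends an immediate message to the DSMB that the vaccine may raise HIV acquisition. The DSMB needs the true false-alarm rate to weigh that message.

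**Working it through.** **Inputs.** Table 6 rows and the 0.014 cut-off (SAP 10.1.1). From Protocol 6.4.1: 2,600 women randomized 1:1; 14-month accrual at half rate for the first 3 months; 10% annual dropout; placebo incidence 4.2% per year, with 3.1% and 5.5% as alternatives; HIV testing about every 3 months. The null is VE = 0, so each infection falls in the vaccine arm with probability 1/2.

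**Step 1: reproduce the stated 5%.** Let q(n,k) be the probability of k vaccine infections among n without having stopped. Before removing stopped paths,

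q(n,k) = ½·q(n−1,k) + ½·q(n−1,k−1).

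From n = 10, paths at or above the boundary are removed and their probability is added to the error. At n = 10 only 10–0 stops, as printed. After that the boundary is the smallest k with P(Bin(n,½) ≥ k) ≤ 0.014. At n = 60, P(X ≥ 39) = 0.0137 and P(X ≥ 38) = 0.0259, which gives Table 6's 39–21. The cumulative error through infection 60 is **0.0499**, so the stated 5% reproduces and is fully used at that point.

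**Step 2: how far testing now runs.** The last enrollee reaches Month 13 at trial month 14 + 13 = 27. Mean entry time is (1.5/12.5)·1.5 + (11/12.5)·8.5 = 7.66 months, so mean time since entry at that point is 19.3 months, or 1.61 years. A hand approximation without diagnosis delay is

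2600 · 0.042/(0.042 + 0.10) · (1 − e^(−0.142·1.61)) ≈ 157.

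Simulation without the delay gives about 156. With diagnosis at the next scheduled visit, the median is **143** (95% range about 121 to 167). The same simulation gives 188 MITT infections for all of Stage 1, against a Protocol Table 6-5 median of 190. The 60th infection falls at about trial month 16 (14.3 to 18.0), roughly 11 months before Month 13 of the last enrollee.

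**Step 3: carry 0.014 forward.**

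| Infections | Cumulative error |
|---|---|
| 60 | 4.99% |
| 62 | 4.99% |
| 63 | 5.07% |
| 100 | 6.3% |
| 143 | 7.3% |
| 167 | 7.8% |

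| Annual incidence | Median infections at Month 13 (95% range) | Error averaged over the count |
|---|---|---|
| 3.1% | 107 (87–127) | 6.5% |
| 4.2% | 143 (122–166) | 7.3% |
| 5.5% | 186 (160–212) | 8.1% |

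Even the lowest lower limit, 87, is well past infection 62. Any cut-off from 0.0138 to 0.0144 reproduces every Table 6 row from 10–1 onward and gives 7.3% to 7.4% at 143. Ignoring the visit delay gives about 7.6%.

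**Step 4: compare with the Protocol.** Table 6-4's 4.57% is for monitoring to Month 13, where Table 6 carried forward gives 7.3%. A constant cut-off of 0.0078 gives 4.59%, so the Protocol simulation appears to rest on a stricter boundary. The Protocol's example of 40 among 60 does not settle this, because 40 also crosses a boundary of 39.

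**Step 5: cut-offs that hold 5%.** The last infection at which the error is still within 5% is 143 for 0.0087, 174 for 0.008 and 214 for 0.0070.

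**The case against.** The SAP prints no boundary past infection 60 and calls Table 6 a selection, so the 7% depends on carrying 0.014 forward. The footnote that supports doing so also requires 5% to be kept, and the Protocol's 4.57% suggests that a stricter boundary was simulated. Protocol Figure 6-3 is not visible here, so the boundary used past infection 60 cannot be read. This stands as a limit: it is not shown that the trial operated a 7% rule. It does not rescue the text, because the footnote points to Table 6 and its claim fails past infection 62. If 0.014 is not meant to continue, the later tests have no stated boundary.

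SAP section 6 can be read as a summary deferring to section 10.1. That is fair, but its trigger is still out of date. The version 1.2 change list adds the 13-month condition to Section 10, Table 5, 10.1.1 and 10.1.2, and lists no change to section 6 or Table 6, which probably explains the mismatch.

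The excess is 1.5 to 3 percentage points, in the direction of earlier warning, and the DSMB decides. That limits the severity.

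Timing also matters. The last Month 24 target date was May 25, 2021, so Month 13 fell in mid-2020, while the current SAP is dated July 2022. Recalibration could no longer change the monitoring itself. The boundary used and its true error can still be documented.

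**Conclusion.** The concern holds and should be fixed. The stated 5% is correct for infections 10 to 60 and wrong for the monitoring period the plan now specifies. With 0.014 carried forward, the family-wise error is about 7.3% at 4.2% incidence, and 6.5% to 8.1% over the Protocol's range. This assumes VE = 0, the Protocol's accrual and dropout, and Table 6 read literally. If 9–1 at the 10th infection also stopped (P = 0.0107, below the printed 0.011), the figures would be 5.3% at infection 60 and 7.6% at 143. The 143 is derived from the design inputs, not stated in the documents, but the exceedance does not depend on it: any count above 62 gives more than 5%. The primary efficacy error rate is not affected.

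**What to change.** Choose one option and state it in SAP 10.1.1, Table 5 and Table 6.

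- **(a) Recalibrate.** Set the cut-off so that 5% holds through the upper end of the plausible count at Month 13. About 0.008 holds through 174 infections and covers the 97.5th percentile at 4.2% incidence; about 0.0070 holds through 214 and covers 5.5%. With 0.008, the chance of flagging a true rate ratio of 1.5 by Month 13 falls from about 78% to about 71%, and by infection 60 from 37% to 28%. The second loss matters because early warning is the purpose of the rule.
- **(b) Keep 0.014** and restate the family-wise error as about 7% (6.5% to 8.1%). Power is unchanged, but the 5% in SAP Table 5, Protocol Table 6-3 and Protocol 6.5.1 must change too.

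In either case, replace the limit at the 60th infection and extend Table 6 to about 170 infections, or about 210 if 5.5% incidence is to be covered. Bring SAP section 6, SAP 10.1.1 with Tables 5 and 6, and Protocol 6.5 and 6.5.1 to one trigger, one boundary and one horizon, and state which boundary produced the 4.57%. If monitoring is already complete, record the boundary actually applied after infection 60 and its error over the infections tested. The cost is wording in a few sections and one recalculated table.
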